Exercise Adaptations: Prior to the start of exercise sessions, participants will be questioned on significant changes in symptoms or the presence of new symptoms (such as nausea or fever), which will be used to modify the exercise session (intensity and components) for that day to allow maximum symptom-limited participation. Participants will be encouraged to complete three sessions per week for at least eight weeks during neoadjuvant therapy. Exercise intensity, components, and time will be recorded for each exercise session to guide the exercise specialist in making appropriate exercise adjustments (progression, maintenance, or reduction). Exercise programs have been found to be safe in cancer survivors, even during life-threatening treatments², but safety has not been investigated specifically in the current population. Common risks may include muscular fatigue and soreness, as well as transient increases in treatment-related symptoms. Rarer risks include the possibility of injury due to unknown bone metastases or acute cardiac events. Intensity and acute changes in symptoms will be closely monitored to decrease these risks.

Participants will schedule their sessions with the exercise specialists administering the program, typically taking place between 8AM and 4PM, Monday through Friday, at the

Anschutz Center for Health and Wellness. Adherence will be measured as the percent of scheduled sessions attended. Exercise sessions will also be individualized to participants on a day to day basis, with time and intensity not exceeding that listed above. Prior to the start of exercise sessions, participants will be questioned on significant changes in symptoms or presence of new symptoms (such as nausea or fever), which will be used to modify the exercise session for that day. Exercise intensity, type, and time will be recorded for each exercise session.

Standard Care: Participants in the Standard Care group will receive no exercise intervention, but will continue to receive standard follow-ups, treatments and services from their oncology team. The services that participants receive as standard care include their medical care, symptom control, social worker support, and nutrition.

Participants in all groups will receive \$50 reimbursement for each Visit completed, totalling \$150.00 for all three Visits.

D. Description, Risks and Justification of Procedures and Data Collection Tools:

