Potential Problems and Solutions: Given that no previous studies of preoperative exercise programs exist in patients with pancreatic cancer, the power analysis for the current study was based on the outcomes of a study of preoperative exercise in patients with lung cancer. It is possible that the estimated sample size here will not provide enough power to detect differences in postoperative outcomes. Regardless of statistical significance, outcomes from this study will provide the basis to allow future studies in this population that are adequately powered. Study groups will not be randomized, resulting in a potential selection bias and baseline differences. The decision to design the study as a non-randomized trial was made to improve recruitment for the target patient population and the short duration of the funding period. Analysis of the number of participants who are willing and able to participate in an exercise intervention at the AHW will determine if a randomized trial is feasible and allow a better estimate of a realistic enrollment period. We will interpret our enrollment activity as

follows: if less than 70% of anticipated enrollment is achieved, we will conclude that additional study sites will be needed to enroll sufficient numbers of patients treated with neoadjuvant therapy for pancreatic cancer for formal hypothesis testing in a RCT.

The individualized nature of the exercise program precludes rigorous control of exercise components between participants. An individualized exercise program may increase adherence and will allow adaptability to acute changes in the patients' health status due to treatment- or disease-related symptoms. The neoadjuvant therapy period will vary between participants, resulting in a variable duration of the exercise intervention. The duration of exercise must remain variable to avoid deconditioning that would be caused by a long lapse between the end of the exercise intervention and surgery. Most patients complete 16 weeks of neoadjuvant therapy before surgery, which will result in a typical exercise intervention lasting 12 weeks. We will record the duration of exercise training and neoadjuvant therapy and test these factors as covariates in the analyses of the fitness, function, and stress outcomes.

F. Data Analysis Plan:

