The timeline for this protocol is estimated at 2 years. Data collection (participant recruitment and intervention) is estimated at 1 - 1.5, after which data will be analyzed and manuscripts prepared.

Data Analysis and Anticipated Outcomes: Groups will be compared on demographic variables such as age and gender. Variables that differ significantly will be included in planned analyses as covariates. Statistical significance will be defined as $\alpha \leq 0.05$, however, results will be interpreted cautiously as is warranted for pilot studies⁴⁴. As we expect to be underpowered to test for statistical interactions, multiple tests will be used to assess differences in baseline measures, change scores, and postoperative outcomes between groups. Change scores will be calculated as the difference between Visit 2 and Visit 1. Groups will be compared using non-parametric exact k-sample permutation tests, which are well suited for small sample sizes as they do not rely on typical normal-theory methods⁴⁵.

Aim 1: The feasibility of implementing this intervention will be assessed by quantifying the accrual rate of patients willing and able to participate in the preoperative exercise intervention and individual patients' adherence to the prescribed exercise program (percentage of scheduled sessions attended). Safety will be determined by the number of non-serious and serious adverse events and relatedness of the events to exercise, as described by COMIRB.

Aim 2: Hypothesis 1 – Baseline physical fitness and function measures and change scores will be compared between groups using exact k-sample permutation tests. We anticipate a significant difference in the changes from Visit 1 to Visit 2, with the Exercise group demonstrating maintained or improved physical fitness and function compared to the Control group, with no differences in baseline measures. A secondary analysis will be used to describe the trajectory of changes in physical function from visits 1, 2, and 3.

Hypothesis 2 – Postoperative outcomes will be compared with exact k-sample permutation tests (hospital length of stay) or Fisher's exact tests (hospital readmission) between the Exercise and Control groups. We anticipate the Exercise group to have a significantly lower hospital length of stay and occurrence of hospital readmission compared to the Control group.

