Exploratory Aim: Hypothesis 1 – Baseline psychological stress and systemic inflammatory status measures and change scores will be compared between groups using exact k-sample permutation tests. We anticipate a significant difference in change scores, with the Exercise group demonstrating decreased (improved) psychological stress and improved systemic inflammatory status (decreased CRP, IL-6, sTNFR1 and IIS; increased IL-10) compared to the Control group, with no differences in baseline measures.

Hypothesis 2 – Spearman correlations will be performed between preoperative measures of psychological stress and systemic inflammatory status and postoperative variables. We

anticipate a significant negative correlation between psychological stress and systemic inflammatory status and postoperative outcomes, with lower levels of stress and inflammation associated with improved outcomes in all participants.

G. Summarize Knowledge to be Gained:

Aim 1: The feasibility of future, larger scale implementation of the preoperative exercise program will be assessed primarily by patient adherence to the program, demonstrating patients' ability and willingness to complete the program. The future study of the intervention will be assessed through the measurement of patient accrual, which will provide a reference for the necessary time frame of future studies.

Aim 2: The analyses performed in this aim will reveal 1) how a preoperative exercise intervention affects physical fitness and physical function prior to and after surgery, and 2) whether a preoperative exercise program is associated with improved postoperative outcomes in patients with pancreatic cancer undergoing neoadjuvant treatment. These analyses will also illustrate typical changes in measures of physical fitness and physical function through analysis of the Standard Care group.

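### Weeks of exercise training, which is the treatment dose and naturally zero in controls, is to be tested as a covariate in the Exercise-versus-Control analyses

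*Combined protocol and SAP*

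**What the plan says.** The relevant sentence closes the discussion of variable intervention length in section IV.E, Potential Scientific Problems: "We will record the duration of exercise training and neoadjuvant therapy and test these factors as covariates in the analyses". It names the outcomes concerned: "covariates in the analyses of the fitness, function, and stress outcomes".

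The analyses are defined in section IV.F, Data Analysis Plan. For Aim 2 Hypothesis 1, "Baseline physical fitness and function measures and change scores will be compared between groups" by exact k-sample permutation tests. For Hypothesis 1 of the Exploratory Aim, "Baseline psychological stress and systemic inflammatory status measures and change scores will be compared between groups using exact k-sample permutation tests". The change score is Visit 2 minus Visit 1. The only covariate rule in IV.F concerns demographic variables that differ between the groups.

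On exposure, section IV.C says "Participants in the Standard Care group will receive no exercise intervention". For exercisers it says "Participants will be encouraged to complete three sessions per week for at least eight weeks during neoadjuvant therapy", and IV.E adds "Most patients complete 16 weeks of neoadjuvant therapy before surgery, which will result in a typical exercise intervention lasting 12 weeks".

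The plan does not say how exercise duration is coded in controls, whether it is used only among exercisers, how it is tested, when it is kept, or how it enters a permutation test.

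**The concern.** Weeks of exercise training is the amount of treatment received after assignment, not a baseline characteristic that might confound the comparison. If it is zero in every control and about 12 in exercisers, it carries almost the same information as group. A model holding both must separate the effect of being in the Exercise group from the effect of having exercised, and Aim 2 Hypothesis 1 does not ask for that separation.

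Leaving controls missing instead of zero does not help: they drop out of the model and no group comparison remains.

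At stake are the 400-metre walk (the primary fitness and function outcome), the other function measures and the stress measures. A real benefit could be missed or, when benefit grows with weeks trained, shown with the wrong sign. Section IV.E says the results will be the basis for later, adequately powered studies, so a misleading adjusted estimate would carry forward. Length of stay, readmission and the feasibility aim are not affected.

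**Working it through.** **Inputs from the documents.** 12 per group before attrition, difference 4 days, SD 3, α 0.05, power 0.90 (IV.B; printed there as β); typical training 12 weeks (IV.E); at least 8 weeks encouraged (IV.C).

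**Assumptions.** Duration is 0 in controls. The SD of weeks among exercisers is 2, 3 or 4, because the documents give none. The true effect is 4/3 = 1.33 SD, borrowed from the length-of-stay planning because none is given for fitness outcomes. Tests are two-sided.

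**The plan's own figure.** n = 2(1.960 + 1.282)² × (3/4)² = 11.8, so 12 per group, as stated. The point does not depend on this figure; it only sets the scale.

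**What the adjusted coefficient means.** Write y = a + b·group + c·weeks, with weeks = 0 in controls. Controls have mean a. Exercisers have mean a + b + c·weeks. So b is the group difference at zero weeks of exercise, and weeks is identical to group × weeks, that is, an interaction term. If benefit is constant, b = 1.33 and c = 0. If benefit is proportional to weeks, c = 1.33/12 = 0.11 and b = 0: the whole effect moves out of the group term.

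**Collinearity.** With mean m and SD s among exercisers, r² = (m/2)² / [(m/2)² + s²/2]. For m = 12:

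- s = 2: 36/38, r = 0.97, variance inflation 19, SE multiplied by 4.4
- s = 3: 36/40.5, r = 0.94, variance inflation 9, SE multiplied by 3.0
- s = 4: 36/44, r = 0.90, variance inflation 5.5, SE multiplied by 2.35

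**Power.** Simulation of 20,000 trials per setting: linear model, 12 per group, weeks Normal(12, s) floored at 1, error SD 1. Entries are for s = 2/3/4.

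| How duration is used | Benefit constant over weeks | Benefit proportional to weeks |
|---|---|---|
| Not used | 0.88/0.88/0.88 | 0.87/0.86/0.85 |
| Always included | 0.11/0.17/0.25 (mean estimate 1.32–1.35) | 0.05/0.05/0.05 (mean estimate about 0) |
| Screened alone against the outcome, then kept | kept in 0.85/0.83/0.79; power 0.13/0.20/0.30 | kept in 0.89/0.90/0.92; power 0.06/0.06/0.06 |
| Kept only if significant with group in the model | kept in about 0.05; power 0.86 | kept in 0.11/0.19/0.29; power 0.81/0.73/0.64 |

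In the last cell, counting only results that favour exercise, power is 0.79/0.71/0.61. In the trials where duration is kept, the mean group estimate is −2.7/−1.6/−1.0 SD, the wrong sign.

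**Is it an artefact of the linear model?** No. A Freedman–Lane permutation test with duration as covariate (1,000 trials, 999 permutations each) gives 0.10/0.18/0.23 under constant benefit and 0.04–0.05 under proportional benefit. The unadjusted permutation test gives 0.83–0.90.

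**Sensitivity, duration always included.**

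- Mean of 8 weeks: power 0.18/0.28/0.39 (constant) and 0.05 (proportional).
- Effect of 0.8 SD, counting results that favour exercise: power falls from 0.45–0.47 to 0.06–0.11 (constant) and 0.02–0.03 (proportional).
- 15 per group (3,000 trials per setting): 0.12/0.21/0.30 (constant) and 0.05 (proportional), against 0.92–0.94 unadjusted.

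**The case against.** The strongest reply is that the sentence closes a paragraph about variation in training length among exercisers, so a dose-response within that group may be all that was meant. On that reading there is no harm. The reading is possible, but it is not written. The sentence pairs exercise duration with neoadjuvant-therapy duration, which exists in both groups, and refers to analyses that IV.F defines between groups. If it was the intent, the fix simply records it.

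Second, IV.F names no duration covariate, so the unadjusted permutation test still answers Hypothesis 1. That stands, and it limits the damage. But IV.E promises the covariate for the same outcomes, and nothing says which result prevails if the two disagree.

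Third, the plan says the factors will be tested, not always included, and the near-total losses need forced inclusion or screening without group. This also stands: if duration is kept only when significant beside group and benefit is constant, the loss is about 0.02. The wrong-sign averages come only from the 11–29% of simulated trials in which duration was kept.

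Fourth, the statement "As we expect to be underpowered to test for statistical interactions" most plausibly explains why change scores replace a group-by-time model. It is not a contradiction about duration. It matters only because duration beside group is itself an interaction term, a kind of test the authors expect to be weak.

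Finally, centring weeks within the Exercise group would protect the group estimate: about 1.33 SD, with power 0.85–0.88 at 12 per group. That is a workable alternative, but the plan does not state it.

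**Conclusion.** The concern holds and should be fixed, with moderate confidence. As written, the plan tests treatment dose as a covariate in a treatment comparison, and the adjusted group effect does not answer Aim 2 Hypothesis 1. Given zero coding in controls, that follows from algebra alone.

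The size of the harm depends on the unstated retention rule and on how benefit varies with weeks. It runs from negligible (power 0.88 to 0.86) to almost total (0.85–0.87 to 0.05). Those figures rest on the assumed SD of weeks and a borrowed effect size, so they illustrate scale and do not predict this trial's fitness results. The direction did not change across the settings tried. This is a defect in the covariate plan, not the loss of the main analysis.

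**What to change.** Amend the sentence in section IV.E to say that exercise-training duration will not enter any Exercise-versus-Control analysis. It will be examined only within the Exercise group as a descriptive dose-response, for example a Spearman correlation of weeks trained with the Visit 2 minus Visit 1 change score. Neoadjuvant-therapy duration exists in both groups, lacks this defect and may remain; confining it to a sensitivity analysis is optional.

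The cost is one sentence. No data collection, patient burden or sample-size figure changes, and the dose information is kept.

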Hypothesis 1: Measures of psychological stress and systemic inflammatory markers will decrease in response to preoperative exercise compared to standard care.

Hypothesis 2: Preoperative measures of psychological stress and systemic inflammatory markers will be positively correlated with postoperative hospital length of stay and occurrence of readmission in all participants.

II. Background and Significance:

The Problem: Interventions to improve health status in patients with pancreatic cancer are understudied. Health, as defined by the World Health Organization, is “a complete state of physical, mental, and social well-being, and not merely the absence of disease or infirmity.” Pancreatic cancer is often diagnosed at an advanced stage, which has resulted in a 5-year survival rate of less than 5%¹. As such, most research has focused on the disease and curative components of treatment, and not the overall health status of the individual. Investigations of exercise in cancer survivors, an intervention able to address and improve most aspects of health, have specifically focused on cancer populations with high survival rates². Furthermore, advances in the medical treatment of pancreatic cancer have increased 5-year survival rate to 10-30% in patients who

receive surgery³, making this a growing clinical population in which interventions to improve health status are understudied.

The Population: Patients with pancreatic cancer undergoing neoadjuvant therapy. Pancreatic cancer is the fourth leading cause of cancer-related death in the United States, resulting in an estimated 37,390 deaths in 2012⁴. Neoadjuvant therapy (preoperative chemotherapy and radiation) is often prescribed to a subgroup of patients to improve their response to surgery, the best known treatment for the disease. This therapy, however, can reduce physical fitness and function, decreasing the health status of the patient during and after treatment. Reduced preoperative cardiopulmonary fitness may also lead to increased postoperative complications⁵, resulting in further decreases in health status.

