The Intervention: A preoperative exercise program during neoadjuvant treatment, which can improve patient health status during and after treatment. Preoperative exercise has been shown to be safe and effective at improving physical fitness and function, vital components of overall health, in patients with other cancer diagnoses undergoing neoadjuvant therapy⁶, but has not been investigated in patients with pancreatic cancer. Therefore, a gap in the research exists surrounding interventions to improve health status in the growing clinical population of pancreatic cancer survivors. The preoperative neoadjuvant treatment period allows implementation of an exercise program likely to maintain or improve cardiovascular fitness and muscular strength, improving postoperative outcomes and health status, and improved physical function has also been associated with decreases in hospital length of stay and readmission⁷. Beneficial effects of preoperative exercise may be mediated by changes in psychological stress and systemic inflammatory markers. Both increased psychological stress and systemic inflammatory markers have been associated with accelerated disease progression and worsening health status^{8,9}. Both are beneficially affected by exercise^{9,10}, possibly contributing to the overall effects of the exercise intervention. Regardless of effects on disease progression, the beneficial psychological effects of exercise¹¹ can contribute to improved health status.

Preoperative exercise is a safe intervention in patients with advanced cancer. Exercise programs, both pre and postoperative, have been safely implemented in a wide variety of cancer survivors, with few to no adverse events reported¹². Although no studies of preoperative exercise programs for patients with pancreatic cancer have been published, postoperative exercise programs in this population have reported no adverse events^{10,13}. A survey of colorectal surgeons agreed that suitable preoperative exercise programs pose no risk to elderly colorectal cancer patients¹⁴, and a systematic review of exercise during neoadjuvant treatment stated that preoperative exercise was a safe and feasible intervention⁶.

III. Preliminary Studies/Progress Report:

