Hospital length of stay will be collected from medical records and be defined as the number of days from surgical admission to hospital discharge.

Hospital readmission will be assessed as whether a patient is rehospitalized in an unplanned response to a surgical complication within 30 days of hospital discharge. Planned rehospitalizations will not be assessed as a hospital readmission.

Hospital physical function will be assessed using the AM-PAC test of inpatient physical activity and basic mobility³⁰.

Questionnaire/Psychological Outcomes Assessment:

Fatigue will be assessed using the Functional Assessment of Chronic Illness Therapy - Fatigue scale (FACIT-Fatigue), a validate measure of fatigue in cancer survivors³¹.

Health-related Quality of Life (HRQOL) will be assessed with the Functional Assessment of Cancer Therapy-General form (FACT-G)³². This form provides information on the physical, social, emotional, and functional well-being of patients with cancer.

Subjective psychological stress will be assessed with the Perceived Stress Scale (PSS)³³, which assesses *perceived stress* based on individual and environmental stressful events, focusing on experiences in the last month. *Depression* will be assessed using the Center for Epidemiologic Studies Depression Scale (CES-D)³⁴.

Prior physical activity level will be assessed with the Godin Physical Activity Questionnaire. This measure is a self-report estimate of leisure physical activity for the prior month. Prior physical activity level will be compared between groups and considered as a potential factor to control for in statistical analyses. This will only be collected at the first assessment.

Objective Stress Assessment:

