The potential participant population will be individuals who receive a diagnosis of borderline-resectable pancreatic cancer (adenocarcinoma), being treated at the University Hospital Cancer Center. These inclusion and exclusion criteria will apply to participants in both groups.

Inclusion Criteria: Recent (< 4 week) first diagnosis of a borderline-resectable pancreatic adenocarcinoma, assigned to receive neoadjuvant therapy and surgery at University of Colorado Cancer Center, physician clearance to participate in exercise program, and age 21-80 years.

Exclusion Criteria: Any significant comorbid conditions that would interfere with or preclude participation in an exercise intervention, including orthopedic conditions such as advanced osteoarthritis, mobility-limiting amputations or chronic injuries, or mobility-limiting acute orthopedic injuries; advanced rheumatoid arthritis; widespread chronic pain conditions such as fibromyalgia; pulmonary conditions such as chronic obstructive pulmonary disease, emphysema, interstitial lung disease, use of supplemental oxygen; known cardiovascular disease, uncontrolled hypertension, or new cardiac event within the past 6 months. Participants with a second cancer diagnosis at the time of enrollment will be excluded.

Sample size estimation: No studies have previously investigated the effects of preoperative exercise in patients with pancreatic cancer. In patients with lung cancer, a preoperative exercise program reduced hospital length of stay by 4 days compared to usual care⁴⁰. Based on this difference, with a SD of 3, 12 participants would be required in each the experimental and control groups ($\alpha = 0.05$, $\beta = 0.90$ ⁴¹). To account for overall attrition, groups will be increased by 3 participants each, based on a study of preoperative exercise after neoadjuvant treatment in patients with rectal cancer showing an overall attrition of 28%⁴². A total of **30 participants (15 per group)** will be recruited for this study.

C. Study Design and Research Methods

This is a prospective, non-randomized, parallel group, intervention control trial, patterned on a similar pilot study in patients with rectal cancer⁴².

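### Covariates for the non-randomised length-of-stay comparison must pass a low-powered significance screen, the named tests have no covariate term as specified, and baseline fitness enters only on a broad reading of the rule

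*Combined protocol and SAP*

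**What the plan says.** Section IV.C describes a non-randomised parallel-group design. Eligible volunteers willing to exercise form the exercise group; those who cannot take the programme on, for reasons such as travel or distance, form the control group. Section IV.E acknowledges that selection bias and baseline differences may follow.

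The analytic response is in section IV.F: "Groups will be compared on demographic variables such as age and gender", followed directly by "Variables that differ significantly will be included in planned analyses as covariates". Significance is set at 0.05. For the surgical results the plan states "Postoperative outcomes will be compared with exact k-sample permutation tests (hospital length of stay") and Fisher's exact test for readmission. It describes no stratified, residual-based or model-based version of either test.

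Baseline fitness and function are compared between groups under Aim 2, Hypothesis 1, but no sentence expressly carries them into the length-of-stay analysis. Section IV.A adds, for self-reported activity, "Prior physical activity level will be compared between groups and considered as a potential factor to control for in statistical analyses", without a criterion.

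Section II gives the reason fitness matters: "Reduced preoperative cardiopulmonary fitness may also lead to increased postoperative complications", and "improved physical function has also been associated with decreases in hospital length of stay and readmission". Length of stay is also the outcome behind the sample size in section IV.B: "Based on this difference, with a SD of 3, 12 participants would be required in each the experimental and control groups".

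**The concern.** Without randomisation, covariate adjustment is the plan's only stated analytic protection against measured differences between the groups. Three features weaken it for length of stay.

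- Whether a variable is adjusted for depends on its baseline p-value. In a sample this small, that p-value is a poor guide to how much the variable biases the comparison.
- Once a variable is selected, the plan does not say how it enters a permutation test or a Fisher test. Two analysts could follow the text and report different adjusted results.
- The measured characteristic that the background section ties most directly to surgical recovery is covered only if the word for what is screened extends beyond demographics.

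Length of stay has no baseline value, so a change score cannot absorb an initial difference. At stake is a biased estimate of the effect on which the trial was sized. Section IV.E intends the results to inform later, adequately powered studies, so the bias could be carried into their planning.

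**Working it through.** **Inputs from the documents.** Difference 4 days, SD 3 days, 12 evaluable and 15 recruited per group (section IV.B); α = 0.05 (sections IV.B and IV.F). The test is taken as two-sided, and the stated β of 0.90 is read as power.

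**Inputs assumed, because the documents give none.** Between-group imbalance d = 0.5 to 0.8 SD; correlation of the covariate with length of stay r = 0.3 to 0.7.

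**1. The plan's own figure.** n = 2(1.960 + 1.282)² × 3² / 4² = 11.82, rounded up to 12 per group. This matches. Power at 12 per group by the t distribution is 88%; at 15 it is 94%.

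**2. Power of the baseline screen.** Two-sample t test with 2n − 2 degrees of freedom and noncentrality d√(n/2).
- n = 12, d = 0.5: 0.5 × √6 = 1.22 against a critical value of 2.07; power 22%.
- n = 15, d = 0.5: 0.5 × √7.5 = 1.37 against 2.05; power 26%.
- n = 12, d = 0.8: 1.96; power 47%.
- n = 15, d = 0.8: 2.19; power 56%.

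The observed imbalance must exceed 2.07 × √(2/12) = 0.85 SD (n = 12) or 2.05 × √(2/15) = 0.75 SD (n = 15) to be significant. For gender by Fisher's exact test, power is about 10% for 40% against 60%, and 39-43% for 30% against 70%.

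**3. Effect on length of stay with no true treatment effect.** If one confounder is left out, expected bias is r × d × SD. The smallest case is 0.3 × 0.5 × 3 = 0.45 days and the largest 0.7 × 0.8 × 3 = 1.68 days. Simulation (40,000 runs per scenario, t test or linear model standing in for the permutation test) gives bias in days and false-positive rate:

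| n per group, d, r | Left out | Screened | Always adjusted |
|---|---|---|---|
| 12, 0.5, 0.3 | 0.45; 6.3% | 0.25; 5.1% | 0.0; 4.9% |
| 12, 0.5, 0.7 | 1.05; 12.8% | 0.59; 5.8% | 0.0; 5.2% |
| 12, 0.8, 0.5 | 1.20; 15.7% | 0.41; 6.1% | 0.0; 5.0% |
| 15, 0.8, 0.7 | 1.68; 31.7% | 0.45; 6.9% | 0.0; 5.1% |

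Over the whole grid, a variable left out gives 0.4-1.7 days and 6-32%, a screened variable 0.2-0.6 days and 5-7%, and one always adjusted about 0 days and 5%. A permutation test in the third row, with the confounder left out, gave 15.1% against 15.7%, so the stand-in is adequate.

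**4. More than one confounder.** For uncorrelated confounders the biases add with their signs. Two with d = 0.8 and r = 0.5 acting the same way give 1.2 + 1.2 = 2.4 days unadjusted. Acting in opposite ways they give 1.2 − 1.2 = 0. The larger totals therefore need confounders that push in the same direction.

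**The case against.** The strongest reply is that controls are controls for practical reasons, not because they are unfit, and that both groups need physician clearance and meet the same eligibility criteria. That makes a large fitness imbalance less likely. It does not exclude one, and section IV.E allows for baseline differences.

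The fitness evidence is also indirect. Section II speaks of preoperative fitness and of function, whereas Visit 1 comes before neoadjuvant therapy that typically lasts 16 weeks and can itself lower fitness. The correlation of Visit 1 walk time with length of stay is therefore an assumption. This stands.

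The trial is a pilot with feasibility as its first aim, and it promises cautious interpretation. That limits the harm, but caution about p-values does not remove bias from an estimate.

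Always adjusting is not always more accurate. With one confounder at d = 0.5, r = 0.3 and n = 12, the root-mean-square error is about 1.3 days both under the screen and with two covariates always in the model. At r of 0.5 or more, always adjusting does better.

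Three stronger readings are tempting, and the documents do not support them.
- A reader might infer that baseline fitness has no route into the analysis at all. That holds only if the rule is confined to demographics; the wording also permits a broad reading.
- A reader might infer that the screening rule itself inflates false positives to around a third. That figure belongs to a strong confounder left out altogether; for a screened variable the rate stays at 5-7%.
- A reader might infer that permutation tests cannot be adjusted. They can; the plan does not say how.

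**Conclusion.** The point holds and should be fixed before analysis; it does not undermine the feasibility aim. Two parts rest on the text and on arithmetic from the stated sample size: the screen misses most imbalances of 0.5 SD and about half of those of 0.8 SD, and the adjusted analysis is undefined.

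The consequence for length of stay is conditional on the assumed imbalance and correlation. For one confounder, the screened bias of up to 0.6 days is 0.6/4 = 15% of the planning difference, and the bias from one left out, up to 1.7 days, is 1.7/4 = 43%. The second figure applies to fitness only on the demographics-only reading. The main harm is bias rather than false positives. Several confounders make it worse only if they act in the same direction, and no covariate rule removes selection on factors outside the model.

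**What to change.** For length of stay, replace the significance screen with one or two covariates named before the data are seen, for example age and Visit 1 400-metre walk time, both already collected. Fit a linear model with group and these covariates, and take the p-value from a residual permutation (Freedman-Lane). Report the planned unadjusted exact test alongside. Label the Fisher test for readmission as unadjusted. State that selection on unmeasured factors remains. Other adjusted methods, such as a stratified permutation test, would also serve; what matters is that the covariates and the method are fixed in advance.

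The cost is a few sentences in the analysis plan, modest programming, and an adjusted p-value that is approximate rather than exact (simulated false-positive rate 4.5-5.4%, including skewed lengths of stay).

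The adjusted analysis also loses some power if the covariates are not prognostic. For 4 days and SD 3, two covariates unrelated to length of stay lower power from 88% to about 84% at 12 per group with no imbalance, and to 79% or 72% if both are imbalanced by 0.5 or 0.8 SD. At 15 per group it falls from 94% to 92%, or to 88% or 83% with those imbalances. If each covariate correlates 0.3 with length of stay and there is no imbalance, power rises slightly, to 90% and 96%. A single covariate costs less but leaves any bias from the other.
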